Study Title: Promoting informed decisions about colorectal cancer screening in older adults

(PRIMED Study): A cluster randomized trial

**Document Title:** Design and Analysis plan for the cluster randomized trial in the PRIMED Study

PIs: [name] ([contact]) and [name] ([contact]) Statisticians: [name]; [name]

Clinical Trials.gov: NCT03959696

**Date:** July 27, 2022

*Purpose:* The goal of the study was to advance our understanding of how to ensure that older adults are well-informed and involved in decisions about whether or not to continue CRC screening. Refer to the study protocol for an outline of the methods used in the study.

*Design:* The PRIMED study is a multi-site cluster randomized trial that enrolled primary care physicians and assigned them to Intervention or Comparator arms. The Intervention arm involved completion of a CME-provided 2-hour online training course in SDM communication skills and received an electronic reminder of patients with an upcoming appointment who are eligible for a CRC screening discussion. Comparator arm physicians received electronic reminders only. Each clinician will complete a baseline survey and a telephone-based SPI to capture baseline SDM skills before patient enrollment begins. Patients and physicians were surveyed after an eligible visit to assess outcomes. After enrollment is complete, all clinicians will participate in a debrief interview.

Physicians were recruited from internal medicine and family medicine practices affiliated with five hospital networks—three academic medical centers and two community hospitals—located in Massachusetts and Maine. They were eligible if they had at least 20 patients aged 75-85 due for a CRC screening or surveillance in their panel. Physicians were enrolled from May to August 2019.

Patients were enrolled from October 2019 through April 2021 (due to COVID-19, patients were

not enrolled from March 13, 2020-May 24, 2020). Eligibility criteria for patient participants are

listed in Table 1.

# Table1. Eligibility for patient participants

#### Eligible

- Adults, age 76-85 at the time of the scheduled visit
- Scheduled for non-urgent office visit with a participating physician during the study period
- Due for discussion or confirmation regarding colorectal cancer screening (e.g. never been screened, <1 year to follow-up interval indicated on previous test).

#### Ineligible

- Prior diagnosis of colon or rectal cancer, inflammatory bowel disease or genetic disorder that raises CRC risk (e.g. hereditary nonpolyposis CRC and familial adenomatous polyposis)
- Unable to consent for themselves (e.g. moderate to severe dementia or other major cognitive limitations)
- Physician excludes based on life threatening diagnosis (e.g. currently being treated for metastatic cancer) or other major event.
- Unable to read or write in English or Spanish

*Randomization and blinding*: Eligible physician participants were grouped into strata based on self-reported gender, years in practice, prior exposure to SDM training (self-reported by physicians at enrollment), and site. Within each stratum, the study statistician used a computer random number generator to randomly assign each physician to either the intervention or control arm. Study staff assessed participating physician schedules every week to identify eligible patients to invite into the study to receive a survey to measure patient-reported outcomes. Patients who completed a survey were followed after 12 months to track colon cancer screening tests completed and a subset were eligible for a telephone interview. The PIs and the project manager were not blinded to physicians' assignment as they needed to arrange access to training

course. The biostatistician was blinded to study assignment and received a de-identified list of participating physicians to generate the assignments. Research staff were blinded both to the name and randomization status of the physician when coding the SPI. Research staff who entered the patient survey data into REDCap and the biostatistician conducting the analyses were blinded.

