The study staff and the principal investigator at each site will have routine meetings during the study period to ensure the project proceeds as intended per the protocol. All participant screening and enrollment will be tracked on password protected servers using an Access or RedCap database. The information is stored behind a firewall and only study staff will have access to it as needed. We will track recruitment rates and response rates weekly and identify issues as they come up. The study staff will complete all required documents for the study binder and this will be reviewed quarterly by the project manager and one of the principal investigators.

Limited data will be kept on clinician non-responders for those who received an individual invitation (site, age, gender, patient volume and years in practice) as well as patient non-responders including age, gender, physician, and all elements in the eligibility screener. This information will be used to examine non-response bias.

For guidance, refer to the following Partners policies: Data and Safety Monitoring Plans and Quality Assurance https://partnershealthcare- public.sharepoint.com/ClinicalResearch/DSMP in Human Subjects Research.pdf

Reporting Unanticipated Problems (including Adverse Events) https://partnershealthcare-

public.sharepoint.com/ClinicalResearch/Reporting Unanticipated Problems including Adverse Events.pdf

PRIVACY AND CONFIDENTIALITY

Describe methods used to protect the privacy of subjects and maintain confidentiality of data collected. This typically includes such practices as substituting codes for names and/or medical record numbers; removing face sheets or other identifiers from completed surveys/questionnaires; proper disposal of printed computer data; limited access to study data; use of password-protected computer databases; training for research staff on the importance of confidentiality of data, and storing research records in a secure location.

NOTE: Additional measures, such as obtaining a Certificate of Confidentiality, should be considered and are strongly encouraged when the research involves the collection of sensitive data, such as sexual, criminal or illegal behaviors.

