### Patient Outcomes:

- Screening uptake: study staff examined medical records to determine receipt of any colorectal cancer screening test for all subjects within 12 months of the index visit.
  The following measures were collected in the patient survey:
  - SDM Process Scale: This 4-item measure assessed the discussion of 1) stopping screening as an option, 2) reasons to screen, 3) reasons not to screen, and 4) patients' screening preference. Individual items were summed to generate a total score (0-4), with higher scores indicating greater shared decision making. Score was calculated if all 4 items were answered and patients who indicated no discussion of CRC received a score of 0.
  - Risk perceptions: One item assessed affective risk perception, or cancer worry. This item will be adapted from the National Cancer Institute's Health Information National Trends Survey (HINTS).
  - Knowledge: Seven multiple choice knowledge items, adapted from the Colorectal Cancer Screening Decision Quality Instrument, were scored. A total knowledge score (0-100%) were calculated if at least half of the knowledge items (4 or more) were answered with the missing items considered as incorrect.

- Screening preference: One item asked patient's preferred approach to screening (with responses: colonoscopy, stool-based test, no screening, and not sure).
- Overall health: patients self-reported overall physical and mental health (PROMIS Scale v1.2-Global Health Physical 2a (poor to excellent).
- Patient's screening intention: One item assessed how likely the patient was to follow through with their preferred approach on a 5-point scale from Definitely will to Definitely will not.
- Screening recommendation and time spent: One item will assess the physician's recommendation about CRC screening (colonoscopy, stool-based test, no further testing, other) and one item will assess if time was spent discussing CRC screening in the visit (yes/no) and if discussed, how much time was spent (<2 minutes, 2-5 minutes, > 5 minutes).
- Single item literacy screener: reported as percentage who never or rarely require help reading medical information indicating high health literacy
- Satisfaction: One item asked "Overall, how satisfied were you with the visit" on a 4-point scale from Extremely satisfied to Not at all satisfied.

Additional data were collected to describe the sample including

- Demographics: race, ethnicity, employment, marital status and education

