*Sample Size*: The study was powered to detect a small to medium effect size difference in the primary outcome, SDM process score. With 500 surveys (250 per arm), assuming an intraclass correlation coefficient of 0.03, the effective patient sample size was estimated at 394, which would enable detection of a difference of 0.28 standard deviations with 80% power and a two-sided significance level of 0.05.

*Statistical methods*: Responders and non-responders were compared to examine potential non-response bias using two-sample t-tests or chi-square tests. Patient sample characteristics were compared between arms using two-sample t-tests or chi-square tests. Multivariable regression models were used to adjust for potential effects of any unbalanced variables.

The following hypotheses were evaluated using an intention to treat approach, and patient outcomes were analyzed based on their physicians' assigned arm regardless of whether the physician completed the training, received the reminder, or discussed CRC screening.

 Examine the effects of the interventions on patients' SDM Process scores and knowledge score:

- a. Compared to the Comparator group, patients seen by physicians in the Intervention arm would report higher SDM Process scores (primary outcome) : We will examine the distribution of the SDM Process score and apply variable transformation techniques if necessary. We will use linear regression models with the Generalized Estimating Equations (GEE) techniques to account for the patients within clinician data structure. We will be able to difference of 0.28 SD for the SDM Process score with 80% power. Studies using the SDM Process survey have found effect sizes ranging from 0.39SD – 0.88SD when comparing sites that used have formal decision support (coaching or decision aids) and those that did not. Although we have sufficient power to detect a smaller difference, we are interested in a meaningful difference 0.4SD or higher.

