- b. Compared to the Comparator group, patients seen by physicians in the Intervention arm would have greater knowledge: We will use linear regression with GEE to compare the mean knowledge score between the two arms. The target sample size will provide 80% power to detect a difference of 0.28 SD for the knowledge scores after adjusting for the effects of clustering. Although there are no standards for a minimally important difference in knowledge, SDM studies have found effect sizes of 0.25SD-0.8SD in studies of decision aids, and this study is adequately powered to detect a meaningful difference in that range, and
- Examine the effects of the interventions on patients' preferences for screening, the extent to which patients receive their preferred approach to screening, and on CRC screening rates.

- a. Compared to the Comparator group, patients seen by physicians in the Intervention arm will receive their preferred approach to screening (either colonoscopy, stool-based test, or no further screening). For these analyses, we will compare the percentages of patients who prefer to stop screening, the percentages of informed patients who received their preferred screening in the 12 months after the visit, and overall rates of screening across the two groups using logistic regression model with the GEE approach to adjust for clustering of patients within clinicians. We will have 81% power to detect a difference of 14% in rates (e.g. decrease from 61% to 47%).
- b. Both interventions will reduce screening rates compared to concurrent controls (rates of clinicians not involved in study). The screening data will be available for all patients from all participating sites. We estimate a total of 6248 patients will be eligible for screening from 436 clinicians: 5353 patients from clinicians not participating the study and 448 from each arm of clinicians participating the study. After taking into account clustering effect, we will have at least 86% power to detect a 6% decrease in CRC screening rates of patients from clinicians participating.
- 3. Examine the effects of the interventions on physicians' confidence and demonstration in their SDM skills and their satisfaction.

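### The randomized comparison of 12-month screening rates rests on survey completers, although the SAP plans screening data for all patients and specifies them only against non-study clinicians

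*SAP*

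**What the plan says.** Four statements in the SAP bear on who contributes to the screening outcome.

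- Randomization and blinding: "Patients who completed a survey were followed after 12 months to track colon cancer screening tests completed".
- Patient Outcomes: "study staff examined medical records to determine receipt of any colorectal cancer screening test for all subjects within 12 months of the index visit". The SAP does not say who the subjects are.
- Statistical methods, 2a: the arms are compared on "overall rates of screening across the two groups using logistic regression model with the GEE approach", with clustering by clinician. No population is named. The power statement is 81% for 61% versus 47%.
- Statistical methods, 2b: "The screening data will be available for all patients from all participating sites". The numbers are "5353 patients from clinicians not participating the study and 448 from each arm of clinicians participating the study". The comparison described is with clinicians not in the study.

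The Protocol is broader. Its Specific Aims promise screening rates compared between arms and against concurrent and historical controls, without naming the population. Research Design and Methods tracks 12-month screening for participating patients and also for participating and non-participating clinicians. It describes rates aggregated at clinician, practice and network level from administrative, billing and clinical data.

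**The concern.** Physicians were randomized. Training and reminders act on every eligible patient they see, whether or not that patient later returns a questionnaire. Survey return follows the visit. Under the COVID-19 recruitment procedure even the first invitation follows it, so a visit shaped by the assigned arm can influence who enters the analysis.

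For preference to stop screening and for receipt of the preferred approach this cannot be avoided, because the survey supplies the preference. Overall screening uptake comes from the record and does not need the survey. Restricting it to completers brings post-randomization selection into a comparison that could avoid it, and uses fewer patients. The larger data set, which includes both randomized arms, is specified in the SAP only for a non-randomized contrast.

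**Working it through.** **Inputs.** Survey sample, ICC and effective size come from SAP Sample Size: "With 500 surveys (250 per arm), assuming an intraclass correlation coefficient of 0.03, the effective patient sample size was estimated at 394". About 10 patients per clinician and about 60 clinicians come from the Protocol. Rates of 61% and 47% come from SAP 2a. For the all-patient data, SAP 2b says: "We estimate a total of 6248 patients will be eligible for screening from 436 clinicians". That is 6248/436 = 14.3 patients per clinician. (5353 + 448 + 448 = 6249; the difference of one is rounding.) The SAP gives no ICC for screening, so applying 0.03 to it is an assumption.

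**Formulas.** Design effect = 1 + (m − 1) × ICC. Effective n = n / design effect. Two-sided 5% power for two proportions with n per arm is Φ{[|p1 − p2| − 1.96 √(2 p̄(1 − p̄)/n)] / √([p1(1 − p1) + p2(1 − p2)]/n)}, where p̄ is the mean of p1 and p2.

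**Step 1: reproduce the plan's figures.** With m = 10, the design effect is 1 + 9 × 0.03 = 1.27 and 500/1.27 = 393.7, matching 394. Per arm n = 196.9. For 61% versus 47%, p̄ = 0.54:

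(0.14 − 1.96 × 0.0502)/0.0497 = 0.835, so power = 79.8%.

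With m = 500/60 = 8.3, the effective total is 410 and power is 81.4%. The stated 81% therefore fits the clustered survey sample. It does not fit 250 per arm without clustering (88.3%), nor the 448 per arm of 2b (94.6% in Step 2).

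**Step 2: both arms, all patients.**

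| Sample | m | Design effect | Effective n per arm | Power, 61% vs 47% | Detectable difference from 61%, 80% power |
|---|---|---|---|---|---|
| 250 per arm (survey) | 10 | 1.27 | 197 | 79.8% | 14.0 points |
| 448 per arm | 14.3 | 1.40 | 320 | 94.6% | 11.0 points |
| 448 per arm | 20 | 1.57 | 285 | 92.1% | 11.6 points |

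The row with m = 20 is there because clinicians needed at least 20 potentially eligible patients to join, so 14.3, an average over all 436 clinicians, may be too low for participants. An 11-point difference has about 59% power in the survey sample (m = 10).

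**Step 3: other ICCs (assumed).** With m = 10 for the survey sample and 896/60 = 14.9 for all patients, the detectable differences are:

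- ICC 0.01: 13.0 versus 9.9 points
- ICC 0.03: 14.0 versus 11.1
- ICC 0.05: 15.0 versus 12.1
- ICC 0.10: 17.2 versus 14.4

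The gain is about 3 points throughout.

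**Step 4: dilution.** The 448 are described as eligible for screening, not as having had a visit. If patients without a visit are unaffected by arm and a fraction v had one, a 14-point effect in visited patients appears as 14v points overall. The all-patient contrast keeps 80% power for it only if v is at least 11.0/14.0 = 0.79 (m = 14.3) or 11.6/14.0 = 0.83 (m = 20).

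**The case against.** A reader might infer that all record follow-up is confined to survey completers. The documents do not support that. The Protocol and SAP 2b plan screening rates for all patients of study clinicians, and the SAP's outcome definition may be meant to cover more than completers. The established problem is narrower: one sentence restricts the tracking, another leaves its population undefined, and 2a is powered on the survey sample.

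Nor can it be said that no between-arm use of the wider data was ever intended, because the Protocol's aims mention rates across arms. The SAP, however, does not specify such an analysis.

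A reader might also infer that the sickest patients are lost from follow-up for testing harms. No figure supports this, and the aggregated rates list neither complications nor deaths, so adding the all-patient contrast would not address it. That argument is not made here.

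Consent is implied by survey return, which may explain the limit on chart review. This stands for hand abstraction. It does not bar the proposed contrast, since 2b already uses screening data on patients who returned no survey, including those of non-study clinicians.

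Some mitigation is planned: repeated reminders, a second packet and completion by phone. The SAP also compares responders with non-responders, and the Protocol keeps limited data on "patient non-responders including age, gender, physician, and all elements in the eligibility screener". But the SAP states no by-arm comparison of response and no correction for it.

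Finally, the between-arm screening rate is not one of the Protocol's numbered hypotheses, and two of the three comparisons in 2a need the survey. That limits the weight of the point without removing it.

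**Conclusion.** The point holds in this limited form. As written and as powered, the randomized comparison of overall 12-month screening rates rests on survey completers, a group formed after randomization and after the visit, for an outcome that needs no survey. The SAP already plans data on a wider population in both arms but does not specify the randomized contrast in it.

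The gain in precision is approximate: a detectable difference of about 11 to 12 points instead of 14 at ICC 0.03. It rests on the SAP's 448 per arm, on an assumed 14.3 to 20 patients per participating clinician, and on most of those patients having had a visit. Below roughly 80% visited, dilution would cancel the precision gain, although freedom from survey selection would remain. It does not follow that the responder comparison is biased: with no response rate, neither the size nor the direction of selection can be computed. This is a secondary outcome. The change is worth making because it is cheap.

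**What to change.** 1. In SAP Patient Outcomes, define *all subjects* for screening uptake and reconcile it with the sentence on 12-month tracking under Randomization and blinding.
2. In 2a, state the analysis population for each of the three comparisons. Keep preference to stop and receipt of the preferred approach in survey completers.
3. In 2b, add the Intervention-versus-Comparator contrast of screening rates in all eligible patients of randomized physicians, with clustering by clinician.
4. Report that contrast beside the chart-reviewed responder result.

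The cost is SAP wording and one further contrast in a model already planned. Because arm is a property of the clinician, clinician-level counts of eligible and screened patients would suffice.

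The downsides should be stated with the result. Electronic screening status is coarser than chart review. The Protocol describes it as the percentage up to date, which may not be anchored to an index visit. Some included patients may have had no visit, which would dilute any effect.

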### Patient Outcomes:

- Screening uptake: study staff examined medical records to determine receipt of any colorectal cancer screening test for all subjects within 12 months of the index visit.
  The following measures were collected in the patient survey:
  - SDM Process Scale: This 4-item measure assessed the discussion of 1) stopping screening as an option, 2) reasons to screen, 3) reasons not to screen, and 4) patients' screening preference. Individual items were summed to generate a total score (0-4), with higher scores indicating greater shared decision making. Score was calculated if all 4 items were answered and patients who indicated no discussion of CRC received a score of 0.
  - Risk perceptions: One item assessed affective risk perception, or cancer worry. This item will be adapted from the National Cancer Institute's Health Information National Trends Survey (HINTS).
  - Knowledge: Seven multiple choice knowledge items, adapted from the Colorectal Cancer Screening Decision Quality Instrument, were scored. A total knowledge score (0-100%) were calculated if at least half of the knowledge items (4 or more) were answered with the missing items considered as incorrect.

- Screening preference: One item asked patient's preferred approach to screening (with responses: colonoscopy, stool-based test, no screening, and not sure).
- Overall health: patients self-reported overall physical and mental health (PROMIS Scale v1.2-Global Health Physical 2a (poor to excellent).
- Patient's screening intention: One item assessed how likely the patient was to follow through with their preferred approach on a 5-point scale from Definitely will to Definitely will not.
- Screening recommendation and time spent: One item will assess the physician's recommendation about CRC screening (colonoscopy, stool-based test, no further testing, other) and one item will assess if time was spent discussing CRC screening in the visit (yes/no) and if discussed, how much time was spent (<2 minutes, 2-5 minutes, > 5 minutes).
- Single item literacy screener: reported as percentage who never or rarely require help reading medical information indicating high health literacy
- Satisfaction: One item asked "Overall, how satisfied were you with the visit" on a 4-point scale from Extremely satisfied to Not at all satisfied.

Additional data were collected to describe the sample including

- Demographics: race, ethnicity, employment, marital status and education
- Family history of colorectal cancer and personal history of prior polyp removal.
- Patients' attitude: self-report of importance of finding cancer early, their feelings regarding the risk & benefits of screening for colon cancer, how much they believe screening will help, single-item maximizer/minimizer scale, tolerance of uncertainty

